Study Endpoints	
The adult and pediatric populations will be combined for primary analysis. Separate secondary analyses also will be performed for the adult and pediatric cohorts. CGM metric analyses will be analyzed separately for the challenge days and subsequent nights and not included in the overall analyses.
 
Primary Safety Endpoints:
 
 
• Severe hypoglycemia (with cognitive impairment such that assistance of another individual is needed for treatment) during study compared with data on severe hypoglycemic events reported by T1D Exchange clinic registry over a 3-month time period.
 
• Diabetic ketoacidosis
 
• Unanticipated adverse device effects
 
• Other serious adverse events
 
• Adverse drug reactions
 
 
Secondary Safety Endpoints:
 
 
• All adverse events (including infusion site reactions)
 
• CGM hypoglycemia outcomes (compared with baseline run-in data and separately when possible with 4 weeks of pre-study CGM data collected at enrollment) 
 
◆ Overall % time <54 mg/dL
 
◆ Postprandial % time <54 mg/dL (30 min, ≤1, ≤2, ≤4, >1 to ≤2 and >2 to ≤4hr)
 
◆ Overall and postprandial % time <70 mg/dL
 
◆ Rate of hypoglycemia events defined as 15 or more consecutive minutes <54 mg/dL
 
 
 
 
Exploratory:
 
 
• Postprandial incremental area under the glucose curve (4 hr)
 
• Peak postprandial glucose
 
• Times in ranges-overall and postprandial (70-180 mg/dL, >180 mg/dL, >250 mg/dL, 70-140 mg/dL)
 
• Mean glucose
 
• Rate of hyperglycemia events, defined as 90 or more minutes >300 mg/dL within 120 minutes
 

PARTICIPANT AREA	DESCRIPTION
	
 
• Overall variability (CV and SD)
 
• HbA1c change from baseline
 
• Patient-reported outcomes
 
 
Exercise and Meal Challenges:
 
 
• Endpoints will be CGM metrics and safety outcomes as indicated above
 
• Separate analyses conducted for the overnight following the challenge
 

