### 1.1.2 Lyumjev Insulin

Lyumjev™ is a rapid-acting human insulin analog indicated to improve glycemic control in adults with diabetes mellitus. It has a faster onset of action and shorter duration of action than Humalog® (insulin lispro). Insulin lispro appears in the bloodstream approximately 1 minute after injection of Lyumjev, 5 minutes faster than Humalog. In pharmacodynamic euglycemic clamp studies comparing Lyumjev and Humalog, onset of action was 10-min faster and duration of action was 44 minutes shorter with Lyumjev compared to Humalog across all populations and dose range. Lyumjev may be given as part of a multiple daily insulin regimen or administered via continuous subcutaneous insulin infusion. This is the first clinical trial evaluating Lyumjev with Control-IQ technology.

39

40 The differences in insulin lispro PK profiles between LY900014 and Humalog following SC injection  
41 were similar in children, adolescents, and adults. LY900014 demonstrated an accelerated insulin lispro  
42 absorption with a reduction in the late exposure and an overall shorter PK duration compared to Humalog.  
43 Following a single subcutaneous bolus infusion with CSII therapy, there was a trend towards an  
44 accelerated absorption of insulin lispro and the duration of exposure was shorter with LY900014 whilst  
45 maintaining a similar overall exposure and maximum concentration compared to Humalog in children and  
46 adolescents with type 1 diabetes (Lilly Internal data).

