#### Secondary Safety Endpoints

953

- 954 • All reportable adverse events
- 955 • CGM hypoglycemia outcomes
  - 956 ♦ Overall % time <54 mg/dL
  - 957 ♦ Postprandial % time <54 mg/dL (30 min, ≤1, ≤2, ≤4, >1 to ≤2 and >2 to ≤4hr)
  - 958 ♦ Overall and postprandial % time <70 mg/dL
  - 959 ♦ Rate of hypoglycemia events defined as 15 or more consecutive minutes <54 mg/dL

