## Contents

1	Consistency of Statistical Analysis Plan with Protocol .....	6
2	Study Overview .....	6
3	Statistical Hypothesis.....	6
4	Sample Size.....	7
5	Endpoints .....	7
5.1	Key Safety Endpoints.....	7
5.2	Secondary Safety Endpoints.....	7
5.3	Exploratory Endpoints.....	7
6	Calculation of Endpoints .....	8
6.1	Safety Endpoints .....	8
6.2	CGM Endpoints.....	9
6.2.1	Details for Postprandial Periods Not Associated with Meal Challenges .....	9
6.2.2	CGM Use .....	10
6.2.3	CGM Endpoints Following Meal and Exercise Challenges .....	10
6.3	Insulin Endpoints.....	11
6.3.1	Insulin Endpoints during Post-Meal Periods Not Associated with Meal Challenges 11	
6.3.2	Insulin Endpoints Following Meal and Exercise Challenges .....	12
6.4	Closed Loop Use .....	12
6.5	Patient Reported Outcomes .....	12
6.5.1	TRIM-D and TRIM-DD .....	12
6.5.2	ITSQ.....	12
7	Analyses Cohorts .....	12
7.1	Analysis Windows.....	12
8	Statistical Analyses .....	13
8.1	Key Safety Analyses .....	13
8.2	Secondary Safety Analyses .....	13
8.3	Exploratory Analyses .....	14
8.4	Meal and Exercise Challenges .....	14
8.5	Protocol Adherence and Retention Analysis.....	14
9	Baseline Descriptive Statistics.....	15

10	Additional Analyses.....	15
10.1	Device Issues .....	15
10.2	Infusion Site Reactions.....	15
10.3	Open-Loop Basal Rates .....	16
11	Subgroup Analyses .....	16
12	Trial Level Safety Review .....	17
13	Multiple Comparisons.....	17
14	References.....	18
15	T1D Exchange Published Table .....	19

1 **1 Consistency of Statistical Analysis Plan with Protocol**

2 All analyses listed in this document are consistent with study protocol (version indicated on the  
3 version history table).

4 **2 Study Overview**

5 The Tandem t:slim X2 pump with Control-IQ technology is a closed loop automated insulin  
6 delivery system approved by FDA. Lyumjev™ is a rapid acting human insulin analog that has  
7 been shown to improve glycemic control in adults with diabetes. This document outlines the  
8 statistical analyses to be performed for a clinical trial evaluating the impact of Lyumjev used  
9 with the Control-IQ system.

10 The study population includes individuals ages 6 to <81 years old with a diagnosis of type 1  
11 diabetes for at least 1 year who are currently using Control-IQ technology. This is a prospective,  
12 single arm study.

13 **3 Statistical Hypothesis**

14 The primary objective of the study is assessment of safety. Severe hypoglycemia and diabetic  

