### 53 **5.2 Secondary Safety Endpoints**

- 54 • All reportable adverse events
- 55 • CGM hypoglycemia outcomes: overall and during postprandial periods for announced  
56 meals, excluding meal challenges described separately below
  - 57 ○ % time  $<54$  mg/dL
  - 58 ○ % time  $<70$  mg/dL
  - 59 ○ Rate of hypoglycemia events, defined as 15 or more consecutive minutes  $<54$  mg/dL  
60 (overall only)

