### 151 **6.2.1 Details for Postprandial Periods Not Associated with Meal Challenges**

152 The start time of a meal is defined as the time a carbohydrate is entered into the study pump.  
153 CGM data collected in the 4 hours following the start of the meal will be used to compute

154 postprandial CGM metrics. If another carbohydrate is entered less than 4 hours after the carb  
155 entry, then data collected up until the following carb entry will be used to compute CGM  
156 metrics. Meals are defined as the 3 largest carb entries on a calendar day. All postprandial CGM  
157 data will be pooled for each participant when calculating CGM metrics, and metrics will be  
158 calculated separately for the lead-in and treatment periods.

159 Postprandial % time <54 mg/dL and % time <70 mg/dL will be computed using all postprandial  
160 data and data  $\leq 1$ ,  $\leq 2$ ,  $> 1$  to  $\leq 2$ , and  $> 2$  to  $\leq 4$  hours following a meal. All data within these bins  
161 will be pooled across meals for each participant prior to calculating % time <54 mg/dL and %  
162 time <70 mg/dL.

163 Postprandial incremental area under the curve (iAUC) will be calculated using the trapezoidal  
164 method [1]. For each meal the baseline value will be set equal to the most recent CGM glucose  
165 measurement prior to the carb entry. If the most recent measurement occurred more than 15  
166 minutes prior to the carb entry than baseline glucose for that meal will be considered missing and  
167 postprandial iAUC will not be calculated. At least 3 hours of CGM data in the 4-hour  
168 postprandial period must be available to calculate iAUC. For each participant the iAUC  
169 calculated for each meal will be averaged. This will be done separately for the lead-in and  
170 treatment periods.

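### SAP 6.2.1 omits, without explanation, one of the six protocol windows (the first 30 minutes) for postprandial % time <54 mg/dL

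*SAP*

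**What the plan says.** Protocol section 8.4 lists among the secondary safety endpoints "Postprandial % time <54 mg/dL (30 min, ≤1, ≤2, ≤4, >1 to ≤2 and >2 to ≤4hr"). The synopsis repeats the same six windows: "30 min, ≤1, ≤2, ≤4, >1 to ≤2 and >2 to ≤4hr". Neither place says why 30 minutes was chosen. In both, postprandial % time <70 mg/dL is a separate item with no windows of its own.

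SAP 5.2 keeps the endpoint family, "CGM hypoglycemia outcomes: overall and during postprandial periods for announced" meals, but sets no windows. That leaves SAP 6.2.1 to define them. It first fixes the length of the period: "CGM data collected in the 4 hours following the start of the meal will be used to compute" the postprandial metrics, cut short if another carbohydrate entry follows sooner. It then states: "Postprandial % time <54 mg/dL and % time <70 mg/dL will be computed using all postprandial" data, and also over 0–1, 0–2, 1–2 and 2–4 hours, with readings pooled across meals within each participant.

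SAP section 1 declares: "All analyses listed in this document are consistent with study protocol".

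**The concern.** A window that the protocol lists twice under safety has no counterpart in the SAP, and the SAP says nothing about the difference. An analyst who follows the SAP will not produce it, and a reader who trusts SAP section 1 will not know that it is missing.

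The window has a plausible purpose. The purpose of the trial is to assess the safety of Lyumjev in this system, and protocol section 1.1.2 says of Lyumjev: "It has a faster onset of action and shorter duration of action than Humalog". The 30-minute window is the only one that isolates the earliest part of the post-meal period. Without it, any low glucose in that half hour can be seen only after averaging with at least the next half hour. The link between faster onset and this window is an inference, since the documents do not make it.

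**Working it through.** The plan states no figure to reproduce here. The check is a comparison of the two lists, followed by two short calculations.

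**1. Windows for % time <54 mg/dL, side by side**

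| Window after meal start | Protocol (synopsis and 8.4) | SAP 6.2.1 |
|---|---|---|
| 0–30 min | listed | absent |
| 0–1 h | listed | computed |
| 0–2 h | listed | computed |
| 0–4 h | listed | computed, as all postprandial data |
| 1–2 h | listed | computed |
| 2–4 h | listed | computed |

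The SAP's postprandial period is 4 hours, so its all-data result stands in for the protocol's 0–4 h window. The count is 6 − 5 = 1 window missing.

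**2. Does another part of the SAP supply it?** No. SAP 6.2.3 analyses meal challenges over 0–3 h, 3–5 h and overnight. SAP 8.4 declines to compute % time <54 mg/dL for the challenges because the periods are short. The version history describes what changed in versions 2.0, 3.0 and 4.0, and no entry mentions postprandial windows.

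**3. Dilution.** Let D be the excess in % time <54 mg/dL during the first 30 minutes. Assume both half-hours contribute equal data, and let the excess in the second half hour be k × D.

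- Excess seen in the 0–1 h bin = (30 × D + 30 × k × D) / 60 = D × (1 + k) / 2.
- If the excess is confined to the first 30 minutes (k = 0): D × 30/60 = 0.5 D.
- If it persists fully through the hour (k = 1): D, with no dilution.

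For k from 0 to 1, the 0–1 h bin therefore shows between half and all of the early excess. The documents give no value for D or k.

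**4. Data available for a 30-minute bin.** Inputs:

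- Three meals per day (SAP 6.2.1).
- The last 16 days of the lead-in, and a minimum of 24 hours of CGM data, stated for postprandial periods (SAP 6.2).
- One meal and one exercise challenge in the lead-in, at least 48 hours apart (protocol 2.5), with challenge days excluded (SAP 6.2).

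Results for the lead-in, at most:

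- No challenge day inside the 16 days: 16 × 3 × 0.5 h = 24 h.
- Two challenge days removed: 14 × 3 × 0.5 h = 21 h.
- For comparison, the existing 0–1 h bin with two days removed: 14 × 3 × 1 h = 42 h.

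The first case can arise because the lead-in may run to 21 days, so both challenges can fall before the last 16. Even then, 24 h is reached only if no reading is missing. If the 24-hour minimum were applied to each bin, a 30-minute lead-in metric could not be computed for a participant with two challenge days removed, and would need perfect data otherwise. The existing bins do not have this problem when data are reasonably complete.

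**The case against.** The strongest reply is that little is lost. The endpoint itself survives: five of six windows are computed, and readings from the first 30 minutes enter the 0–1 h, 0–2 h and all-data results. Overall % time <54 mg/dL and the rate of CGM hypoglycemia events are also kept. The study's success criterion rests on severe hypoglycemia and DKA, which this bin does not touch. All of that stands, and it limits the weight of the point.

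A reader might infer that a secondary safety endpoint has been dropped altogether. The table above shows otherwise: one sub-window is missing.

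A reader might also infer selective reporting, because SAP version 4.0 is dated after follow-up was complete. The documents do not support that. The version history records no removal after version 1.0, which is dated before enrollment began. The natural reading is that the bin was never in the SAP, which makes this a drafting mismatch made before any data existed.

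A third tempting step is to say that early lows are expected in the first half hour. The documents do not say so. The onset difference in protocol 1.1.2 comes from clamp studies. The rationale in protocol 1.2 expects faster onset to reduce high glucose after meals, and shorter duration possibly to reduce hypoglycemia.

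One might argue that the short-period reason in SAP 8.4 covers this window too. It is given only for single challenges. Ordinary meals are pooled over many days, so it does not carry over.

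What remains unanswered is the mismatch itself: the protocol asks for the window, the SAP does not provide it, and the SAP says the two agree.

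**Conclusion.** The point holds as an undeclared mismatch between protocol and SAP that should be corrected. One of six listed windows for a secondary safety endpoint will not be reported if the SAP is followed. The consequence is loss of resolution, not loss of the endpoint: on the assumptions in step 3, the 0–1 h bin shows at least half of any excess in the first 30 minutes. It does not affect the success criterion, and it is no evidence of results-driven selection.

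The conclusion assumes that the protocol text reviewed is the version 4.0 that the SAP cites, which cannot be confirmed because the title page was removed. It also assumes that the bin was absent from SAP version 1.0, which is inferred from the revision descriptions because the earlier SAP versions are not available.

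**What to change.** - Add a 0–30 minute bin for % time <54 mg/dL to SAP 6.2.1, pooled across meals like the other bins. A matching bin for <70 mg/dL is optional, since the protocol attaches the windows only to <54 mg/dL.
- State in SAP 6.2 that the 24-hour minimum applies to the postprandial period as a whole, or set a separate minimum for this bin that the lead-in can meet.
- Date the change and label it as made after follow-up was complete.
- If the bin is not restored, declare and justify its removal, and correct the consistency statement in SAP section 1.

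The cost is one more bin in existing code, using data already collected, one sentence on the data minimum, and one more endpoint in the secondary safety group for false discovery rate control (SAP section 13).

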### 171 **6.2.2 CGM Use**

172 The percentage of time using CGM will be calculated during the treatment period by dividing the  
173 amount of time the CGM was used by the total follow-up time in the period. The amount of  
174 CGM use will be determined based on the number of readings available (each reading represents  
175 5 minutes of use). Readings taken from 12:00 AM on the day after the baseline visit until 11:59  
176 PM on the day prior to the date of the 13-week visit will be used to calculate CGM use for  
177 participants who complete the study. For participants dropped from the study, readings taken  
178 from 12:00 AM on the day after the baseline visit until 11:59 PM on the date prior to study  
179 withdrawal will be used to calculate CGM use.

### 180 **6.2.3 CGM Endpoints Following Meal and Exercise Challenges**

181 Participants will complete 1 meal and 1 exercise challenge during the lead-in period and 3 meal  
182 and exercise challenges during the treatment period. The following CGM metrics will be  
183 computed before, during, and after meal and exercise challenges:

- 184 • Time in Ranges 70-180 mg/dL, 70-140 mg/dL, >180 mg/dL, >250 mg/dL
- 185 • Mean Glucose
- 186 • Glucose CV
- 187 • Glucose SD
- 188 • Peak Glucose (meal challenge only)
- 189 • Nadir Glucose (exercise challenge only)
- 190 • Postprandial iAUC (computed for 3 hours following meal challenges only, following the  
191 method described in Section 6.2.1)
- 192 • The proportion of participants with at least one CGM hypoglycemic event < 54 mg/dL
- 193 • The proportion of participants with at least one CGM value < 70 mg/dL

- 194 • Time in ranges < 70 mg/dL, <54 mg/dL (overnight period only)
- 195

196 For meal challenges, CGM data collected between the start of the challenge and 3 hours  
197 following the start, between 3 hours after the start of the challenge and 5 hours after the start of  
198 the challenge, and in the overnight period (12 AM to 5:59 AM) on the following day will be used  
199 to compute CGM metrics. The times provided in the study logbook will be used as the start and  
200 end times of the meal challenge. Metrics will be computed separately for each of the 3 meal  
201 challenges during the treatment period. At least 75% of CGM data must be available in each  
202 period for metrics to be analyzed for that period.

203 For exercise challenges, CGM data collected between the start of the challenge and 2 hours after  
204 the start, between 2 hours after the start of the challenge and 4 hours after the start of the  
205 challenge, and in the overnight period (12 AM to 5:59 AM) on the following day will be used to  
206 compute CGM metrics. Metrics will be calculated separately for each of the 3 exercise  
207 challenges during the treatment period. At least 75% of CGM data must be available in each  
208 period for metrics to be analyzed for that period.

### 209 **6.3 Insulin Endpoints**

210 The insulin metrics listed in Section 5.3 will be calculated during the lead-in period and  
211 treatment period. The sum of basal, bolus, and total (basal+bolus) insulin delivered will be  
212 calculated on each calendar day, and then averaged within each study period to calculate the  
213 average daily insulin doses. Average daily insulin doses will be divided by the participants  
214 weight (in kg) to get the dose in units/kg. Metrics will be calculated over 24 hours, during the  
215 daytime (6:00 AM to 11:59 PM) and nighttime (12:00 AM to 5:59 AM), and after meal and  
216 exercise challenges. At least 20 hours of basal insulin data will be required on a given day for  
217 24-hour metrics to be calculated, at least 15 hours are required for daytime metrics, and at least 5  
218 hours are required for nighttime metrics. At least 1 day with sufficient insulin data is required  
219 during a period to calculate insulin metrics for that period. 24-hour, daytime, nighttime, and post-  
220 prandial insulin metrics will not include daytime and following nighttime insulin data on days  
221 with meal or exercise challenges; these will be analyzed separately. Insulin data from periods  
222 during the treatment phase where Humalog was used will not be included in the calculation of  
223 insulin metrics.

#### 224 **6.3.1 Insulin Endpoints during Post-Meal Periods Not Associated with Meal Challenges**

225 For each participant the average postprandial basal, bolus, and total insulin will be calculated.  
226 Insulin data collected in the 4 hours after a meal will be used to calculate insulin metrics for that  
227 meal. At least 3 hours of insulin data must be available during the postprandial period for metrics  
228 to be calculated. If another carb entry occurs within 4 hours of the meal, then insulin data  
229 collected until the next carb entry will be used. The sum of basal, bolus, and total (basal+bolus)  
230 postprandial insulin delivered will be calculated on each calendar day, and then averaged within  
231 each study period to calculate average daily postprandial insulin metrics.

232 **6.3.2 Insulin Endpoints Following Meal and Exercise Challenges**

233 For each meal and exercise challenges the amount of basal, bolus, and total insulin delivered will  
234 be calculated for each participant. Insulin metrics will be computed for the same time periods  
235 discussed in Section 6.2.3. At least 75% of insulin data must be available during the challenge  
236 for metrics to be calculated. Insulin metrics will be calculated separately for each of the 3 meal  
237 and exercise challenges occurring during the treatment period. The start and end times of the  
238 meal and exercise challenges will be determined from the study logbooks.

239 **6.4 Closed Loop Use**

240 The percentage of time the control IQ system was used in closed loop mode during the treatment  
241 period will be calculated. This will be done by summing the total amount of time in closed loop  
242 mode from 12:00 am the day after the training visit to 11:59 pm on the day prior to the 13-week  
243 visit and dividing by the total follow-up time. For participants who drop from the study, data  
244 between 12:00 am on the day after the training visit to 11:59 pm on the day prior to study  
245 withdrawal will be used to calculate closed loop use. The same will be done for open loop,  
246 exercise, and sleep modes.

247 **6.5 Patient Reported Outcomes**

248 **6.5.1 TRIM-D and TRIM-DD**

249 In the TRIM-D and TRIM-DD questionnaires all items are scored on a 5-point Likert scale. For  
250 the total score and subscale scores, a raw score will first be calculated by summing across items.  
251 Raw scores are then transformed to a 0 to 100 scale by using the following formula:

252 
$$\frac{\text{Raw Score} - \text{Lowest Possible Raw Score}}{\text{Range of Possible Raw Scores}} \times 100$$

253 If any items are unanswered the total score and subscale pertaining to that item will not be  
254 calculated.

255 **6.5.2 ITSQ**

256 Items on the ITSQ are scored on a 7-point Likert scale. The raw total score and subscale scores  
257 are computed by calculating the mean across all non-missing item scores. Scores are then  
258 transformed to a 0 to 100 scale by using the following formula:

259 
$$\frac{7 - \text{Raw Score}}{6} \times 100$$

260 At least 75% of items must be non-missing to calculate scores.

261 **7 Analyses Cohorts**

262 All participants who initiate the treatment and provide at least 24 hours of CGM data will be  
263 included in the analyses.

264 **7.1 Analysis Windows**

265 The central lab HbA1c measured at the end of the lead-in period must be collected within 21  
266 days before to 7 days after the Lyumjev training visit, and the HbA1c measured at the end of the

267 treatment period must be collected within 42 days before to 30 days after the 13-week target date  
268 (91 days after the Lyumjev training visit). HbA1c measurements collected outside the analysis  
269 windows will be treated as missing.

270 The PRO outcomes at screening must be collected prior to the Lyumjev training visit, and PRO  
271 outcomes at 13 weeks must be collected within 42 days before to 30 days after the 13-week  
272 target date (91 days after the Lyumjev training visit). PRO outcomes collected outside the  
273 analysis windows will be treated as missing.

